8.3 Off-Agent Criteria

Participants may stop taking study agent for the following reasons: completed the protocol-prescribed intervention, adverse event or serious adverse event, inadequate agent supply, noncompliance, concomitant medications, or medical contraindication. Participants who experience complications of pancreatitis or develop intercurrent pancreatitis during the study will be instructed to continue taking the study agent unless they are unable to take oral medications. The study agent will be resumed as soon as they are able to tolerate oral medications. Participants will continue to be followed, if possible, for safety reasons and in order to collect endpoint data according to the schedule of events.

As described in section 7.5, clinical research staff will make follow-up telephone calls to the participants on days 30 ± 7 , 60 ± 7 , and 90 ± 7 after the participant discontinues the study agent to assess symptoms and adverse events. Standard of care data (medical history, laboratory test results, concomitant medications, imaging results) will continue to be collected via review of the participant's electronic medical record at the time points specified in the Schedule of Time and Events. If feasible, we will conduct a research visit to collect final measurements for participants who permanently discontinue the study agent early. An end-of-study research visit will be conducted 6 months after initiation of the statin intervention (Study Visit 3). The blood collections for clinical labs and banked samples future research, and the follow-up risk questionnaire will not be done. The following procedures will be performed during the end-of-study visit:

1. Review medical history, medications, and laboratory test results
2. Vital signs assessment, measurement of weight, and symptom assessment
3. ECOG performance status

4. Pregnancy test for women of child-bearing potential. Women who have had a hysterectomy, both ovaries removed, or a tubal ligation will not be required to have a pregnancy test.
5. Blood collection for measurement of protocol-specific biomarkers (6 mL): serum concentrations of the following targets: interleukins (IL; 1 α , 1 β , 1RA, 2, 4, 5, 6, 7, 8, 9, 10, 12p40, 12p70, 13, 15, 17A, 17F, 18, 21, 22, 27, 23, 31), BDNF, CD40L, EGF, ENA78, Eotaxin, FASL, FGF β , GCSF, GMCSF, GROA, HGF, ICAM1, IFN α , IFN β , IFN γ , IP10, LIF, Leptin, MCP1, MCP3, MCSF, MIG, MIP1 α , MIP1 β , PDGF β , PIGF1, NGF, Rantes, Resistin, PAI1, SCF, SDF1 α , TGF α , TGF β , TNF α , TNF β , TRAIL, VCAM1, VEGF, VEGFD.
6. Fecal specimen for measurement of fecal elastase. A stool collection kit and instructions will be provided to the participant before the scheduled visit. The specimen will be self-collected at home.
7. Self-administered QLQ-C30 and QLQ-PAN28(CP) to assess quality of life and pain level.
8. Endoscopic pancreatic function test (ePFT) and simultaneous endoscopic ultrasound (EUS) and fasting pancreatic fluid to measure secretin-stimulated peak bicarbonate concentration; and concentrations of the following targets: interleukins (IL; 1 α , 1 β , 1RA, 2, 4, 5, 6, 7, 8, 9, 10, 12p40, 12p70, 13, 15, 17A, 17F, 18, 21, 22, 27, 23, 31), BDNF, CD40L, EGF, ENA78, Eotaxin, FASL, FGF β , GCSF, GMCSF, GROA, HGF, ICAM1, IFN α , IFN β , IFN γ , IP10, LIF, Leptin, MCP1, MCP3, MCSF, MIG, MIP1 α , MIP1 β , PDGF β , PIGF1, NGF, Rantes, Resistin, PAI1, SCF, SDF1 α , TGF α , TGF β , TNF α , TNF β , TRAIL, VCAM1, VEGF, VEGFD.

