5.6 Dose Modification

No dose modifications are planned. The study agent will be stopped in the event of an AE \geq grade 3 considered possibly, probably, or definitely related to the study agent. The study agent will be restarted after resolution. One of the common side effects of statin medication is myalgia (muscle pain with normal creatine phosphokinase (CPK) level), and rarely this is associated with statin myopathy (muscle weakness or other muscle injury with or without elevation in CPK level). In randomized controlled trials of standard dose statin therapy, the risk is very low (<1%). We will measure levels of CPK in the blood drawn at the first study visit to establish a patient-specific reference for this indicator of muscle toxicity. During the trial, if the participant reports unexplained muscle pain or weakness, CPK will be tested again to check for elevation. The study agent will be temporarily discontinued in subjects experiencing grade 1 or greater myopathy (unexplained muscle symptoms *and* creatine phosphokinase (CPK) > 2.5 times institutional ULN) or hepatotoxicity (ALT or AST > 1.5 times institutional ULN) that is considered possibly, probably, or definitely related to the study agent. Resolution of myopathy or hepatotoxicity will be evaluated with follow-up laboratory blood tests 4 weeks after the elevated levels occur. If the lab test results are still elevated after 4 weeks, the study agent will be discontinued permanently and the participant's primary care physician will be notified of the abnormal tests. If the lab test results return to normal levels, participant will go back on the study agent.

Because dose modification could lead to lack of dose homogeneity that may impair the research objectives, we will stop the intervention in patients who initiate drugs that require dose modifications of simvastatin below 40 mg: lomitapide, verapamil, diltiazem, dronedarone, amiodarone, amlodipine, or ranolazine.

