6.2 Reported Adverse Events and Potential Risks

The most common (incidence $\geq 5.0\%$ patients) reported adverse events (AEs) are upper respiratory infection, headache, abdominal pain, constipation, and nausea. Other AEs reported in clinical trials ($<5\%$) were diarrhea, rash, dyspepsia, flatulence, and asthenia.

Persistent increases in serum transaminases (to more than 3 x ULN) have occurred in approximately 1% of patients who received simvastatin in clinical studies. When drug treatment was interrupted or discontinued in these patients, the transaminase levels usually fell slowly to pretreatment levels. The increases were not associated with jaundice or other clinical signs or symptoms. It is recommended that liver function tests be performed before the initiation of treatment, and thereafter when clinically indicated.

Simvastatin occasionally causes myopathy manifested as muscle pain, tenderness or weakness with creatine kinase above 10 x ULN. Myopathy sometimes takes the form of rhabdomyolysis with or without acute renal failure secondary to myoglobinuria, and rare fatalities have occurred. Predisposing factors for myopathy include advanced age (≥ 65 years), female gender, uncontrolled hypothyroidism, and renal impairment. The risk of myopathy, including rhabdomyolysis, is dose related. The risk of myopathy and rhabdomyolysis is increased by high levels of statin activity in plasma. Simvastatin is metabolized by the cytochrome P450 isoform 3A4 (CYP3A4). Certain drugs which inhibit this metabolic pathway can raise the plasma levels of simvastatin and may increase the risk of myopathy. These include itraconazole, ketoconazole, posaconazole, voriconazole, the macrolide antibiotics erythromycin and clarithromycin, and the ketolide antibiotic telithromycin, HIV protease inhibitors, boceprevir, telaprevir, the antidepressant nefazodone, cobicistat-containing products, or grapefruit products. Combination of these drugs with simvastatin is contraindicated. If short-term treatment with strong CYP3A4 inhibitors is unavoidable, therapy with simvastatin must be suspended during the course of treatment.

Increases in HbA1c and fasting serum glucose levels have been reported with HMG-CoA reductase inhibitors, including simvastatin.

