11.1.3 Severity of AEs

11.1.3.1 Identify the AE using the CTCAE version 4.0. The CTCAE provides descriptive terminology (MedDRA lowest level term) and a grading scale for each AE listed. A copy of the CTCAE can be found at http://ctep.cancer.gov/protocolDevelopment/electronic_applications/ctc.htm.

AEs will be assessed according to the grade associated with the CTCAE AE term. AEs that do not have a corresponding CTCAE term will be assessed according to the general guidelines for grading used in the CTCAE v4.0. as stated below.

CTCAE v4.0 general severity guidelines:

Grade	Severity	Description
1	Mild	Mild; asymptomatic or mild symptoms; clinical or diagnostic observations only; intervention not indicated.
2	Moderate	Moderate; minimal, local or noninvasive intervention indicated; limiting age-appropriate instrumental activities of daily living (ADL)*.
3	Severe	Severe or medically significant but not immediately life-threatening; hospitalization or prolongation of hospitalization indicated; disabling; limiting self-care ADL**.
4	Life-threatening	Life-threatening consequences; urgent intervention indicated.
5	Fatal	Death related to AE.

ADL

*Instrumental ADL refers to preparing meals, shopping for groceries or clothes, using the telephone, managing money, *etc.*

**Self-care ADL refers to bathing, dressing and undressing, feeding self, using the toilet, taking medications, and not bedridden.

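### Sections 5.6 and 8.3 conflict on whether to hold the study agent for pancreatitis of grade 3 or higher judged at least possibly related, and neither says which prevails

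*Combined protocol and SAP*

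**What the plan says.** Section 5.6 (Dose Modification) states: "The study agent will be stopped in the event of an AE". The threshold is at or above "grade 3 considered possibly, probably, or definitely related to the study agent", so severity and attribution must both be met. It continues: "The study agent will be restarted after resolution". No exception is made for pancreatitis.

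Section 8.3 (Off-Agent Criteria) deals with pancreatitis by name. Participants who have complications of pancreatitis or who "develop intercurrent pancreatitis during the study will be instructed to continue taking the study agent unless they are unable to take oral medications" are covered whatever the grade or attribution of the episode. For those who had to pause, it adds: "The study agent will be resumed as soon as they are able to tolerate oral medications". The same paragraph opens with a list of reasons for which a participant may stop, including "adverse event or serious adverse event, inadequate agent supply, noncompliance, concomitant medications, or medical contraindication".

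Neither section refers to the other, and no order of precedence is given.

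**The concern.** Both instructions are worded as mandatory, and for one kind of event they cannot both be followed. A site that reads 5.6 would hold the agent until the episode resolves. A site that reads 8.3 would keep the participant on it for as long as medication can be taken by mouth. Each could be cited for a deviation under the other section.

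What is at stake is consistent handling of a participant-safety instruction across four sites, and a clear record of exposure. Section 5.7 makes compliance depend partly on every dose being taken in the week before Study Visits 2 and 3. A participant able to take oral medication whose episode falls in that week could therefore count as compliant if 8.3 is followed and non-compliant if 5.6 is followed.

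The event type is not remote. Section 4.1.1 enrols patients with at least two acute episodes in the past 12 months, and Section 8.2.3 makes pancreatitis-related readmission a secondary endpoint.

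**Working it through.** No formula applies and the plan gives no figure to reproduce. The check sets the trigger conditions side by side and asks whether the overlapping case can arise.

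**Step 1: the inputs.**
- 5.6: stop if the grade is 3 or higher and the event is at least possibly related; restart after resolution.
- 8.3: for intercurrent pancreatitis or complications of pancreatitis, continue unless oral medication is impossible; resume once it is tolerated.
- 11.1.4: five attribution levels. Three (possible, probable, definite) meet the 5.6 condition; two (not related, unlikely) do not.

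**Step 2: the rules applied to a pancreatitis episode.**

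| Grade and attribution | Oral medication possible? | Grade 3 rule in 5.6 | 8.3 | Result |
|---|---|---|---|---|
| Any grade; not related or unlikely | Yes | Not triggered | Continue | No conflict |
| Any grade; not related or unlikely | No | Not triggered | Pause until oral medication is tolerated | No conflict |
| Grade 1 or 2; at least possibly related | Yes | Not triggered | Continue | No conflict |
| Grade 1 or 2; at least possibly related | No | Not triggered | Pause until oral medication is tolerated | No conflict |
| Grade 3 or higher; at least possibly related | Yes | Stop until resolution | Continue | Opposite instructions |
| Grade 3 or higher; at least possibly related | No | Stop until resolution | Pause until oral medication is tolerated | Both interrupt; restart conditions differ |

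In the last row the difference matters when oral intake returns before the episode has resolved. In that interval 8.3 says resume and 5.6 says hold. Section 5.6 explains how resolution is assessed for myopathy and hepatotoxicity, but not for pancreatitis.

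**Step 3: can the last two rows arise?**
- *Recording.* Section 11.1.1 requires all adverse events after consent and the Visit 1 assessments to be recorded whether or not related, and Section 11 does not exempt pancreatitis. Attribution is a required data element (11.1.2).
- *Grade.* The general description of grade 3 in 11.1.3 includes "hospitalization or prolongation of hospitalization indicated", so an episode leading to admission could reach it. That table applies only to events without their own CTCAE term, so the grade of a given episode is an assumption here.
- *Attribution.* Investigators are blinded (6.8), and nothing tells them how to attribute pancreatitis. Section 6.2 gives the agent's common adverse events as "upper respiratory infection, headache, abdominal pain, constipation, and nausea". Abdominal pain and nausea are on that list and pancreatitis is not. A rating of possible is therefore neither excluded nor directed.

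The overlapping case can arise. Its frequency would require the rate of on-study episodes, the share at grade 3 or higher, and the share judged at least possibly related. The documents give none of these.

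**The case against.** The strongest reply is that 8.3 is specific to pancreatitis and 5.6 is a general rule, so the specific one governs. That reading is reasonable, but it is not stated. Section 8.3 does not say that it applies regardless of attribution, and its own opening list includes adverse events and serious adverse events as reasons to stop. Section 5.6 is a safety stop with no stated override.

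A second reply limits the reach of the point, and it stands. A reader might infer that the expected natural-course event, a recurrence, is under two opposite rules. It is not. An episode put down to the underlying disease would be rated not related or unlikely, and only 8.3 then applies. The background in Section 2.3, which reports simvastatin use associated with fewer pancreatitis episodes (rate ratio 0.29), may also incline investigators towards such a rating. Nor does 8.3 always keep participants on the agent: it pauses it when oral medication is impossible.

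A third reply concerns consequences, and it also stands. A reader might infer that interruptions would fall unequally between the arms and distort the Month 6 comparison. The documents do not show this. A hold under 5.6 is followed by restart on resolution, Section 13.5 specifies intention-to-treat analysis, and 8.3 continues endpoint collection off agent where possible. A reader might also apply the 20-30% likelihood of recurrence in Section 2.1 to the sample. That figure has no 6-month window, relates to patients after an episode of acute pancreatitis, and counts all recurrences rather than those in conflict.

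**Conclusion.** The point holds in a confined form. For intercurrent pancreatitis or a complication of pancreatitis that is grade 3 or higher and judged at least possibly related, 5.6 and 8.3 give opposite instructions if oral medication is possible, and different restart conditions if it is not. No precedence is stated. Outside that combination the grade 3 rule in 5.6 and the instruction in 8.3 do not conflict.

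The size cannot be given as a number of participants. That the case will occur at all rests on two assumptions: that some episodes will be graded 3 or higher, and that some of those will be rated possible or above. Neither is implausible, but neither can be quantified from the documents. No bias in the primary comparison is demonstrated.

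The correction is still worth making, because two mandatory safety instructions that cannot both be followed leave sites to choose between them. No view is taken here on which clinical rule is right.

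**What to change.** Reconcile 5.6 and 8.3. State in both which section governs when pancreatitis or its complication is grade 3 or higher and judged at least possibly related, including the condition for restarting, and cross-refer the two. The clinical choice is for the sponsor and medical monitor.

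The cost is about one sentence in each section, with no added visits, procedures or participants. A reason code for interruptions due to pancreatitis on the drug-exposure form is optional. Missed-dose dates are already recorded at telephone calls (5.7, 7.3.2), the diary asks for the reason for a missed dose (Appendix C), pill counts are done at Study Visits 2 and 3, and the adverse event form carries onset date, end date and attribution (11.1.2).

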8.4 Off-Study Criteria

Participants may go 'off-study' for the following reasons:

- Adverse Event
- Death
- Disease Progression
- Lost to follow-up/Participant Withdrawal
- Participant Refused Follow-up
- Physician Decision
- Protocol Defined Follow-up Completed
- Protocol Violation
- Study Complete
- Ineligible
- Other

8.5 Study Termination

NCI, DCP as the study sponsor has the right to discontinue the study at any time.

9. CORRELATIVE/SPECIAL STUDIES

9.1 Rationale for Methodology Selection

Endoscopic pancreatic function test: The current gold standard for diagnosing chronic pancreatitis is the endoscopic pancreatic function test (ePFT) which measures secretin-stimulated production of bicarbonate ion from pancreatic ductal cells during an endoscopic ultrasound procedure (EUS) [3, 32]. Clinically, ePFT-based peak bicarbonate levels can distinguish mild and severe chronic pancreatitis, and is correlated with the extent of histologically determined fibrosis ($r=-0.57$) [33]. Because ePFT is based on an endoscope-guided collection of pure pancreatic fluid, it provides a direct measurement of pancreatic

function that is superior to indirect measurements in stool i.e., fecal elastase [34].

Endoscopic ultrasound: The endoscopic ultrasound is an imaging tool for evaluating the presence or absence of nine ductal and parenchymal criteria for chronic pancreatitis: hyperechoic foci, hyperechoic strands, cysts, lobularity, calcifications, hyperechoic duct margins, visual side branches, main pancreatic duct dilation, and main pancreatic duct irregularity, which sum to a score ranging from 0 to 9 [32]. It is the current standard of care imaging method for determining the extent of chronic pancreatitis.

Immunological cytokines and C-reactive protein: A panel of immunological cytokines will be measured to evaluate the effect of statin on immune profiling markers in the pancreatic fluid and in the blood. We will use the MILLIPLEX MAP Human Cytokine/Chemokine Magnetic Bead Panel- Immunology Multiplex to measure interleukins (IL; 1 α , 1 β , 1RA, 2, 4, 5, 6, 7, 8, 9, 10, 12p40, 12p70, 13, 15, 17A, 17F, 18, 21, 22, 27, 23, 31), BDNF, CD40L, EGF, ENA78, Eotaxin, FASL, FGF β , GCSF, GMCSF, GROA, HGF, ICAM1, IFN α , IFN β , IFN γ , IP10, LIF, Leptin, MCP1, MCP3, MCSF, MIG, MIP1 α , MIP1 β , PDGF β , PIGF1, NGF, Rantes, Resistin, PAI1, SCF, SDF1 α , TGF α , TGF β , TNF α , TNF β , TRAIL, VCAM1, VEGF, and VEGFD.

9.2 Comparable Methods

Proposed methods represent standard technology for measuring the study biomarkers.

10. SPECIMEN MANAGEMENT

10.1 Laboratories

- 1) Study blood tests will be done for a Complete Blood Count and Automated Differential (CDF), a Complete Metabolic Panel (CMPL), a Lipid Panel, hemoglobin A1C, and creatine phosphokinase (CPK) at the clinical laboratories at each study site; or the blood tests will be done at an external CLIA-certified clinical laboratory as required by the participant's health insurance carrier.
- 2) Measurement of bicarbonate concentrations in pancreatic fluid will be performed by Cedars-Sinai Department of Pathology and Laboratory Medicine.
- 3) Study assays for blood and pancreatic fluid concentrations of interleukins (IL; 1 α , 1 β , 1RA, 2, 4, 5, 6, 7, 8, 9, 10, 12p40, 12p70, 13, 15, 17A, 17F, 18, 21, 22, 27, 23, 31), BDNF, CD40L, EGF, ENA78, Eotaxin, FASL, FGF β , GCSF, GMCSF, GROA, HGF, ICAM1, IFN α , IFN β , IFN γ , IP10, LIF, Leptin, MCP1, MCP3, MCSF, MIG, MIP1 α , MIP1 β , PDGF β , PIGF1, NGF, Rantes, Resistin, PAI1, SCF, SDF1 α , TGF α , TGF β , TNF α , TNF β , TRAIL, VCAM1, VEGF, and VEGFD will be performed in the Stanford Human Immune Monitoring Core (HIMC). The lab is equipped with a Luminex MAGPIX multiplexing system which will be used in combination with specific antibody based magnetic bead assays to measure each of the analytes.

10.2 Collection and Handling Procedures

Research study staff at participating study sites will receive specific instructions for collection, processing, and shipment of specimens.

Endoscopic pancreatic function test (ePFT) for collection of fasting pancreatic fluid.

Instructions regarding the endoscopic procedures (Esophagogastroduodenoscopy (EGD) or endoscopic

ultrasound (EUS)) and the collection of fasting pancreatic fluid will be given to participants prior to their study visit. Subjects will be instructed to fast overnight (8 hours) before the testing. Briefly, the ultrasound-adapted endoscope will be replaced with a standard endoscope and fluid from the stomach and duodenum will be removed by aspiration. A test dose of ChiRhoStim[®] human synthetic secretin 0.2 mcg (0.1 mL) is injected intravenously to test for possible allergies. After one minute, if there are no signs of allergic reaction, ChiRhoStim[®] at a dose of 0.2 mcg/kg of body weight is injected intravenously over 1 minute. Pancreatic fluid will be aspirated from the descending duodenum at five time points over one hour (at 0-10 minutes, 10-20 minutes, 20-30 minutes, 30-45 minutes, and 45-60 minutes) following hormonal stimulation. Each collection will contain at least 3 mL of pancreatic fluid, which is sufficient for analysis of peak bicarbonate concentration (*primary endpoint*) and cytokine, chemokine, adhesion molecule concentrations (*secondary endpoint*). For each time point, 1.0 mL of pancreatic fluid will be placed into a plastic collection vial without preservatives and placed in wet ice. The samples will be transported to the designated processing lab for bicarbonate analysis. The remainder of the pancreatic fluid specimen will be stored for later assays of cytokines, chemokines, and adhesion molecules. Immediately upon receipt of the pancreatic fluid, lab personnel will process the specimen as specified in the Laboratory Manual. Processed specimens will be stored in a -80° C freezer awaiting batch analysis.

Fecal specimen. A stool collection kit that includes instructions and supplies for collecting the fecal sample at home will be provided to participants prior to their study visit. The fecal specimen will be self-collected at home and brought to the study visit. Participants will receive a phone call reminder the day before the visit to collect the fecal specimen and bring it to the study visit. The fecal specimen will be processed as specified in the Laboratory Manual and stored at -80°C. .

Blood specimen. A blood specimen (approximately 10 mL) will be collected from each participant at the Screen 2 visit for blood tests to confirm eligibility. A Complete Blood Count (CBC) and a Comprehensive Metabolic Panel (CMPL) will be done to confirm that laboratory levels for acceptable organ, hepatic, and renal function are within the eligibility requirements. See Appendix A for Clinical Laboratory Minimum Test Requirements. If a patient's lab results within 35 days before the Screen 2 visit are available in the medical record and are within eligibility range, their blood will not be drawn at the Screen 2 visit. Otherwise, the patient's blood will be drawn to confirm eligibility.

Approximately 36 mL of blood will be collected from each participant at Study Visits 1, 2, and 3 using a standard phlebotomy protocol. Fasting instructions will be provided to participants prior to their study visit, and participants will receive a phone call reminder the day before the visit to fast overnight (8 hours). The date and time of the blood draw and of the participant's last meal will be recorded.

Approximately 10 mL of blood will be drawn for laboratory blood tests to monitor for potential adverse effects of the intervention and to confirm that laboratory levels meet the eligibility requirements for continuation in the trial. A fasting Lipid Panel will be done at all study visits. A CBDF and a CMPL will be done at Study Visits 2 and 3. If blood tests were not done at the Screen 2 visit for a CBDF and CMPL; and lab results within 30 days prior to Study Visit 1 for these tests are not available in the medical record, a CBDF and CMPL will also be done at Study Visit 1. Fasting Hemoglobin A1C will be measured at Study Visits 1 and 3. Creatine phosphokinase (CPK) will be measured at Study Visit 1. See Appendix A for Clinical Laboratory Minimum Test Requirements.

Twenty-six mL of blood will be collected for research purposes. Six mL of blood will be drawn into a red top serum vacutainer tube for measurement of protocol-specific interleukins (IL; 1 α , 1 β , 1RA, 2, 4, 5, 6, 7, 8, 9, 10, 12p40, 12p70, 13, 15, 17A, 17F, 18, 21, 22, 27, 23, 31), BDNF, CD40L, EGF, ENA78, Eotaxin, FASL, FGF β , GCSF, GMCSF, GROA, HGF, ICAM1, IFN α , IFN β , IFN γ , IP10, LIF, Leptin, MCP1, MCP3, MCSF, MIG, MIP1 α , MIP1 β , PDGF β , PIGF1, NGF, Rantes, Resistin,

PAI1, SCF, SDF1 α , TGF α , TGF β , TNF α , TNF β , TRAIL, VCAM1, VEGF, and VEGFD. Twenty mL of blood will be drawn into three vacutainer tubes, including one 6 mL red top serum tube and two 7 mL lavender top EDTA tubes, for DNA extraction and use in future studies. The blood will be collected and processed as specified in the Laboratory Manual. Processed specimens will be stored at -80°C for later measurement of cytokine concentrations, DNA extraction, and use in future studies.

